3.1 Administration Schedule

Patients will be instructed to take afatinib 40mg PO daily at the same time each day continuously for each 28 day cycle until tumor progression or unless patient experiences unacceptable toxicities.

NOTE: Afatinib tablets are taken once daily. Afatinib tablets should not be chewed nor crushed.

NOTE: Do not take Afatinib with food. Afatinib should be taken at least one hour before food intake, or at least two hours after food intake.

Missed doses should not be administered if within 12 hours of the next scheduled dose. If vomiting occurs after taking a dose of afatinib, the patient should not take an additional dose as a replacement.

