1.1.2 Clinical Pharmacokinetics (PK) and Activity of Afatinib

1.1.2.1 Clinical Pharmacokinetics

Clinical pharmacokinetic data of afatinib were derived from PK data from Phase I/II and III studies with monotherapy or combinations.

Absorption and distribution: Afatinib plasma concentration-time profiles were comparable for the individual dose groups tested (10 to 100 mg), exhibiting at least biexponential disposition kinetics and increased with increasing doses. A moderate to high variability was observed for the plasma concentrations e.g., for the 40 mg dose group with geometric Coefficient of Variations (gCVs) ranging from 50.8 to 221 %. A similar variability range was observed in the other dose groups ranging from 10 to 100 mg. Maximum plasma concentrations mainly occurred at 2 to 5 hours after drug administration. Afatinib exhibited similar disposition characteristics after oral administration at all dose levels after single dose and at steady state, which could be described by at least biexponential disposition kinetics. In cancer patients, afatinib showed a high apparent volume of distribution during the terminal phase both after single dose and at steady state (V_z/F and $V_z/F,ss$) which might indicate a high tissue distribution of the drug. However, the respective values should be interpreted with caution as the absolute bioavailability (F) of afatinib in humans is not known. Plasma protein-binding of afatinib in humans was non-saturable up to 500nM. Binding of afatinib to human serum albumin (45mg/L) was moderate (79.6%). Protein binding was not changed in

mild and moderately liver impaired subjects compared to matched healthy controls.

Food Effect: A food effect study comparing the pharmacokinetics of afatinib (40 mg) administered as tablets to cancer patients revealed that absorption was decreased with a reduction of afatinib gMean Cmax and AUC_{0-∞} values by around 50% and 39%, respectively under fed conditions compared to fasted conditions. Since a statistically significant food effect was observed, afatinib should be taken without food (i.e. food should not be consumed for at least 3 hours before and at least 1 hour after taking afatinib).

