3.4 Dose Modifications

All toxicity grades below are described using the NCI Common Terminology Criteria for Adverse Events (CTCAE) version 4.0.

All appropriate treatment areas should have access to a copy of the CTCAE version 4.0. A copy of the CTCAE version 4.0 can be downloaded from the CTEP website (<http://ctep.cancer.gov>).

Afatinib will be administered at the recommended dose of 40 mg orally once daily starting on the first day of administration and continue until disease progression or unacceptable toxicity. We chose the 40 mg daily dose since the Css still remains adequate at this dose. With the 50 mg dose used in previous trials of afatinib in HER2+, patients showed poor tolerability data. High Rates of dose modification were seen in previous studies with 50 mg daily dosing.

Afatinib will not be held for hematologic toxicity, unless it is determined to be a drug-related grade 3 or 4 hematologic event.

Treatment may be delayed by 2 weeks due to toxicity. If treatment is delayed beyond 2 weeks the subject will come off study for unacceptable toxicity.

Discontinuation of afatinib for any reason for longer than 2 weeks will result in removal of the patient from this subprotocol.

The afatinib dose may be adjusted according to individual patient tolerance as outlined below.

Table 1. Dose Levels for Afatinib

Dose Level	Daily Dose/ Route	Dispensed As	Schedule
Starting dose level: 0	40 mg, PO	1 × 40-mg tablet	Daily during 4-week cycle
-1	30 mg, PO	1 × 30 mg tablet	Daily during 4-week cycle
-2	20 mg, PO	1 × 20-mg tablet	Daily during 4-week cycle

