5.1.7 Route of Administration

Oral. Administer afatinib on an empty stomach; at least 1 hour before or 2 hours after a meal. Missed doses should not be administered if within 12 hours of the next scheduled dose.

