Appendix I

Rev.12/16

Patient Pill Calendar

Storage: Store at Room Temperature

Pill Calendar Directions

1. Take your scheduled dose of each tablet.
2. Please bring the empty bottle or any leftover tablets and your pill calendar to your next clinic visit.
3. Take afatinib on an empty stomach at least 1 hour before or 2 hours after a meal
4. Afatinib tablets are taken once daily. Afatinib tablets should not be chewed nor crushed.
5. Missed doses should not be administered if within 12 hours of the next scheduled dose.
6. Do not take an additional dose as a replacement if vomiting were to occur after taking a dose of Afatinib.
7. Limit time in the sun, sun exposure can cause rash and severe sunburn. Apply sunscreen, wear hat and protective clothing for any sun exposure.

Patient Pill Calendar

This is a calendar on which you are to record the time and number of tablets you take each day. You should take your scheduled dose of each tablet. **Note the times and the number of tablets that you take each day.** If you develop any side effects, please record them and anything you would like to tell the doctor in the space provided. Bring any unused tablets and your completed pill calendar to your doctor's visits.

Afatinib

DAY	Date			Time tablets taken	Dose of tablets taken	Use the space below to make notes about things you would like to tell the doctor (including unusual symptoms you experience, other medicine you have taken and anything else you think would be of interest.)
	Month	Day	Year			
1						
2						
3						
4						
5						
6						
7						
8						
9						
10						
11						
12						
13						
14						
15						
16						
17						
18						
19						
20						
21						
22						
23						
24						
25						
26						
27						
28						

Patient Signature: _____ Date: _____

**Molecular Analysis for Therapy Choice (MATCH)
MATCH Treatment Subprotocol B: Afatinib**

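### Does the 3-hour food interval in the background, against 2 hours in the dosing instructions, call for a change to the plan?

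*Protocol*

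**What the plan says.** Four places in the protocol speak about food.

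- **1.1.2.1 (Introduction, Food Effect)** summarises a study of 40 mg tablets in cancer patients. Cmax and AUC fell "by around 50% and 39%, respectively under fed conditions compared to fasted conditions". The text goes on: "Since a statistically significant food effect was observed, afatinib should be taken without food". In parentheses it explains this as "food should not be consumed for at least 3 hours before and at least 1 hour after taking afatinib".
- **3.1 (treatment plan)** tells patients not to take the drug with food and adds: "Afatinib should be taken at least one hour before food intake, or at least two hours after food intake".
- **5.1.7 (pharmacy section)** says: "Administer afatinib on an empty stomach; at least 1 hour before or 2 hours after a meal".
- **Appendix I (pill calendar)** says: "Take afatinib on an empty stomach at least 1 hour before or 2 hours after a meal".

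The dose is justified by exposure. Section 1.1.2.1 argues that the steady-state concentration at 40 mg exceeds the IC50 for HER2, and 3.4 adds: "We chose the 40 mg daily dose since the Css still remains adequate at this dose".

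**The concern.** The only place that links a food interval to data asks for 3 hours before the dose. The three places that people act on allow 2 hours, cite no source, and do not mention the difference. Because the dose rests on an exposure argument and food lowers exposure substantially, a reader may fear that the operational rule lets in doses taken too soon after a meal. If exposure were lower as a result, the 40 mg rationale would be weaker than it reads, and a disappointing response rate could partly reflect under-exposure. At the least, a reader cannot tell which food conditions the stated exposure assumes.

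**Working it through.** **Intervals side by side**

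| Place | Before the dose | After the dose | Food-free window |
|---|---|---|---|
| 1.1.2.1 (background) | 3 h | 1 h | 3 + 1 = 4 h |
| 3.1 (treatment plan) | 2 h | 1 h | 2 + 1 = 3 h |
| 5.1.7 (pharmacy) | 2 h | 1 h | 2 + 1 = 3 h |
| Appendix I (pill calendar) | 2 h | 1 h | 2 + 1 = 3 h |

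The difference is 4 − 3 = 1 hour, all before the dose. This reads the operational rule as applying to every meal: at least 2 hours since the last one and at least 1 hour until the next. The background joins its two intervals with *and*, the other three places with *or*. Read literally, *or* would let a patient meet one condition and ignore the other, but the instruction to dose on an empty stomach makes the per-meal reading the sensible one.

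**What the food data support.** The study contrasts fed with fasted dosing. The protocol gives no exposure figures at 2 or 3 hours after a meal and does not state the fasting interval used in the study. The 3 hours is offered as an explanation of what *without food* means; it is not calculated from the 50% and 39% reductions. The data therefore support not dosing with food, which all four places require. They do not separate 2 hours from 3.

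**Can the exposure effect be bounded?** Only very loosely. For a dose 2 to 3 hours after food, the AUC loss could lie anywhere from 0 to the fully fed figure of 39%, and the upper end is a state the operational text forbids. Taking that end anyway:

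- Steady-state AUC at 40 mg is 631 ng·h/mL (pharmacokinetic Table 1 in 1.1.2.1).
- 631 × (1 − 0.39) = 384.9 ng·h/mL, and 384.9 / 24 h = 16.04 ng/mL on average.
- The HER2 IC50 is 14 nM (1.1.1). The protocol gives no molecular weight, so only a break-even can be found: 16.04 × 10⁻⁶ g/L ÷ 14 × 10⁻⁹ mol/L ≈ 1,146 g/mol. For total drug, the average concentration exceeds the IC50 at any molecular weight below that.
- If the 79.6% albumin binding in 1.1.2.1 is taken as the bound fraction, free drug is 16.04 × 0.204 = 3.27 ng/mL and the break-even falls to about 234 g/mol.

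The answer depends on whether total or free drug is the right basis, which the documents do not settle. It also describes fed dosing, not dosing 2 to 3 hours after a meal. The calculation neither condemns nor clears the 2-hour rule, and no conclusion here rests on it.

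**Does it reach the analysis?** The available text does not connect the interval to eligibility, response assessment or any analysis set. The pill calendar records the time and dose of tablets but has no column for meal times, so the calendar could not routinely show which interval a patient kept.

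**The case for a change.** The strongest case for acting is that this is a plain contradiction in a dosing instruction. The background sentence says how the drug should be taken, so it is more than description, and it is the only one placed beside data. The four statements are intact current text. One line would remove the conflict, and in a protocol that defends its dose by exposure, a reader deserves to know which food conditions apply.

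Much of that stands. The texts do differ, and the available pages offer no reason. Two parts are weaker. The 3-hour figure stands next to the food data but is not derived from them, so it is no better supported as a benchmark than the 2-hour figure. And the absence of an explanation can be asserted only for the text at hand: the Appendix II patient handout and the Master Protocol, with which this subprotocol must be used, could not be checked.

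What does not follow is a consequence for the trial. The conflict could be cleared entirely by editing or explaining one background sentence, and that would alter nothing that patients do or that the trial concludes.

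**Conclusion.** The discrepancy is genuine but small: one hour before the dose, between a background sentence and three operational places that agree with one another. Every patient in the subprotocol is given the same instruction in the places seen, and it already rules out dosing with food. No loss of exposure, failure of the dose rationale or effect on the analysis is shown, and the documents contain no data that could show one for doses 2 to 3 hours after a meal.

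This is a clerical mismatch, and no change to the plan is called for. The passages should be reconciled, or the difference explained, when the text is next revised; which interval is right is for the clinical and pharmacy team. The conclusion assumes that sites follow the treatment plan, pharmacy section and pill calendar over the introduction, that the operational rule applies to each meal, and that neither the Appendix II handout nor the Master Protocol gives patients a different instruction.

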3.1.1 Potential Drug-drug interaction

Afatinib is a substrate of P-glycoprotein (P-gp). Thus, in patients taking P-gp inhibitors (including but not limited to ritonavir, cyclosporine A, ketoconazole, itraconazole, erythromycin, verapamil, quinidine, tacrolimus, nelfinavir, saquinavir, and amiodarone), or strong P-gp inducers (including but not limited to rifampicin, carbamazepine, phenytoin, phenobarbital or St. John's Wort), which may alter exposure to afatinib, afatinib should be administered simultaneously with or before drugs that affect P-gp.

Because the lists of these agents are constantly changing, it is important to regularly consult a frequently-updated list such as Facts and Comparisons or Lexicomp; medical reference texts such as the Physicians' Desk Reference may also provide this information. The Principal Investigator should be alerted if the subject is taking any agents that are strong P-gp inhibitors or inducers.

3.2 Adverse Event Reporting Requirements

The Adverse Event Reporting Requirements for all EAY131 subprotocols are outlined in the MATCH MASTER protocol. Please refer to those guidelines when determining if an event qualifies as a Serious Adverse Event (SAE) and requires expedited reporting via CTEP's Adverse Event Reporting System (CTEP-AERS).

In addition, the following section outlines agent specific requirements and must be followed to ensure all reporting requirements are met.

3.2.1 Additional instructions, requirements and exceptions for EAY131 – Subprotocol B

Additional Instructions

For instructions on how to specifically report events that result in persistent or significant disability/incapacity, congenital anomaly, or birth defect events via CTEP-AERS, please contact the AEMD Help Desk at [contact] or [contact]. This will need to be discussed on a case-by-case basis.

EAY131 - Subprotocol B specific expedited reporting requirements:

- **Pregnancies:** Pregnancies and suspected pregnancies (including a positive or inconclusive pregnancy test, regardless of age or disease state) occurring while the subject is on Afatinib, or within 28 days of the subject's last dose of Afatinib, are considered immediately reportable events. The pregnancy, suspected pregnancy, or positive/ inconclusive pregnancy test must be reported via CTEP-AERS within 24 hours of the Investigator's knowledge. Please refer to Appendix VIII in MATCH Master protocol for detailed instructions on how to report the occurrence of a pregnancy as well as the outcome of all pregnancies.

EAY131 - Subprotocol B specific expedited reporting exceptions:

For Subprotocol B, the adverse events listed below **do not** require expedited reporting via CTEP-AERS:

- If an AE meets the reporting requirements of the protocol, and it is listed on the SPEER, it should **ONLY** be reported via CTEP-AERS if the grade being reported exceeds the grade listed in the parentheses next to the event.

3.2.2 Second Primary Cancer Reporting Requirements

All cases of second primary cancers, including acute myeloid leukemia (AML) and myelodysplastic syndrome (MDS), that occur following treatment on NCI-sponsored trials must be reported to ECOG-ACRIN using Medidata Rave

- **A second malignancy is a cancer that is UNRELATED to any prior anti-cancer treatment (including the treatment on this protocol). Second malignancies require ONLY routine reporting as follows:**

1. Complete a Second Primary Form in Medidata Rave within 14 days.
2. Upload a copy of the pathology report to ECOG-ACRIN via Medidata Rave confirming the diagnosis.

3. If the patient has been diagnosed with AML/MDS, upload a copy of the cytogenetics report (if available) to ECOG-ACRIN via Medidata Rave.
- **A secondary malignancy is a cancer CAUSED BY any prior anti-cancer treatment (including the treatment on this protocol). Secondary malignancies require both routine and expedited reporting as follows:**
 1. Complete a Second Primary Form in Medidata Rave within 14 days
 2. Report the diagnosis via CTEP-AERS at <http://ctep.cancer.gov>
Report under a.) leukemia secondary to oncology chemotherapy, b.) myelodysplastic syndrome, or c.) treatment related secondary malignancy
 3. Upload a copy of the pathology report to ECOG-ACRIN via Medidata Rave and submit a copy to NCI/CTEP confirming the diagnosis.
 4. If the patient has been diagnosed with AML/MDS, upload a copy of the cytogenetics report (if available) to ECOG-ACRIN via Medidata Rave and submit a copy to NCI/CTEP.

NOTE: The Second Primary Form and the CTEP-AERS report should not be used to report recurrence or development of metastatic disease.

NOTE: If a patient has been enrolled in more than one NCI-sponsored study, the Second Primary Form must be submitted for the most recent trial. ECOG-ACRIN must be provided with a copy of the form and the associated pathology report and cytogenetics report (if available) even if ECOG-ACRIN was not the patient's most recent trial.

NOTE: Once data regarding survival and remission status are no longer required by the protocol, no follow-up data should be submitted via CTEP-AERS or by the Second Primary Form.

Rev. 3/17
Rev. Add21

3.3 Comprehensive Adverse Events and Potential Risks List (CAEPR) for Afatinib (BIBW 2992, NSC 750691)

The Comprehensive Adverse Event and Potential Risks list (CAEPR) provides a single list of reported and/or potential adverse events (AE) associated with an agent using a uniform presentation of events by body system. In addition to the comprehensive list, a subset, the Specific Protocol Exceptions to Expedited Reporting (SPEER), appears in a separate column and is identified with bold and italicized text. This subset of AEs (SPEER) is a list of events that are protocol specific exceptions to expedited reporting to NCI via CTEP-AERS (except as noted below). Refer to the 'CTEP, NCI Guidelines: Adverse Event Reporting Requirements'

http://ctep.cancer.gov/protocolDevelopment/electronic_applications/docs/aeguide_lines.pdf for further clarification. Frequency is provided based on 2596 patients. Below is the CAEPR for Afatinib.

NOTE: If an AE meets the reporting requirements of the protocol, and it is listed on the SPEER, it should ONLY be reported via CTEP-AERS if the grade being reported exceeds the grade listed in the parentheses next to the event in the SPEER.

Version 2.2, April 24, 2019¹

Adverse Events with Possible Relationship to Afatinib (CTCAE 5.0 Term) [n= 2596]			Specific Protocol Exceptions to Expedited Reporting (SPEER)
Likely (>20%)	Less Likely (<=20%)	Rare but Serious (<3%)	
EYE DISORDERS			
	Eye disorders - Other (eye disorders) ²		
GASTROINTESTINAL DISORDERS			
	Cheilitis		
	Constipation		Constipation (Gr 2)
Diarrhea			Diarrhea (Gr 3)
	Dyspepsia		Dyspepsia (Gr 2)
Mucositis oral ³			Mucositis oral³ (Gr 2)
Nausea			Nausea (Gr 2)
		Pancreatitis	
	Vomiting		Vomiting (Gr 2)
GENERAL DISORDERS AND ADMINISTRATION SITE CONDITIONS			
Fatigue			Fatigue (Gr 2)
	Fever		Fever (Gr 2)
HEPATOBILIARY DISORDERS			
		Hepatic failure	
INFECTIONS AND INFESTATIONS			
Infection ⁴			Infection⁴ (Gr 2)
INVESTIGATIONS			
	Alanine aminotransferase increased		

Adverse Events with Possible Relationship to Afatinib (CTCAE 5.0 Term) [n= 2596]			Specific Protocol Exceptions to Expedited Reporting (SPEER)
Likely (>20%)	Less Likely (<=20%)	Rare but Serious (<3%)	
	Aspartate aminotransferase increased		
	Creatinine increased ⁵	Ejection fraction decreased	
	Weight loss		
METABOLISM AND NUTRITION DISORDERS			
	Anorexia		Anorexia (Gr 2)
	Dehydration		Dehydration (Gr 2)
	Hypokalemia		
MUSCULOSKELETAL AND CONNECTIVE TISSUE DISORDERS			
	Muscle cramp		
NERVOUS SYSTEM DISORDERS			
	Dysgeusia		Dysgeusia (Gr 2)
RENAL AND URINARY DISORDERS			
	Renal and urinary disorders- Other (renal impairment) ⁵		
RESPIRATORY, THORACIC AND MEDIASTINAL DISORDERS			
	Cough		Cough (Gr 2)
	Dyspnea		Dyspnea (Gr 2)
	Epistaxis		Epistaxis (Gr 2)
	Nasal congestion	Respiratory, thoracic and mediastinal disorders - Other (interstitial lung disease) ⁶	
SKIN AND SUBCUTANEOUS TISSUE DISORDERS			
	Dry skin		Dry skin (Gr 2)
		Palmar-plantar erythrodysesthesia syndrome	Palmar-plantar erythrodysesthesia syndrome (Gr 2)
	Pruritus		
	Rash acneiform		
	Skin and subcutaneous tissue disorders - Other (nail effect) ⁷		Skin and subcutaneous tissue disorders - Other (nail effect)⁷ (Gr 2)
Skin and subcutaneous tissue disorders - Other (rash) ⁸			Skin and subcutaneous tissue disorders - Other (rash)⁸ (Gr 2)
		Stevens-Johnson syndrome	
		Toxic epidermal necrolysis	

¹This table will be updated as the toxicity profile of the agent is revised. Updates will be distributed to all Principal Investigators at the time of revision. The current version can be obtained by contacting [contact]. Your name, the name of the investigator, the protocol and the agent should be included in the e-mail.

²Ocular disorders may include conjunctivitis, conjunctival irritation, conjunctival hyperemia, corneal abrasions, corneal erosion, dry eye, keratitis, ulcerative keratitis, keratopathy, and xerophthalmia.

³Mucositis oral (stomatitis) may include stomatitis, aphthous stomatitis, mucosal inflammation, mouth ulceration, oral mucosa erosion, mucosal erosion, and mucosal ulceration.

⁴Infection may include any of the 75 infection sites under the INFECTIONS AND INFESTATIONS SOC.

⁵Renal impairment may include acute kidney injury (acute renal failure), acute pre-renal failure, renal impairment, creatinine increased, blood urea increased, glomerular filtration rate increased, and glomerular filtration rate abnormal.

⁶Interstitial lung disease may include acute interstitial pneumonitis, pneumonitis, acute respiratory distress syndrome, pulmonary infiltrates, and pulmonary fibrosis.

⁷Nail effect includes paronychia and nail disorder (e.g., nail ridging, nail loss, and nail discoloration).

⁸Rash may include rash, rash pustular, folliculitis, skin fissures, skin exfoliation, dermatitis, erythema, skin reaction, skin ulcer, skin toxicity, skin erosion, skin irritation, and skin swelling.

Adverse events reported on afatinib trials, but for which there is insufficient evidence to suggest that there was a reasonable possibility that afatinib caused the adverse event:

BLOOD AND LYMPHATIC SYSTEM DISORDERS - Anemia; Bone marrow hypocellular

EAR AND LABYRINTH DISORDERS - Vertigo

GASTROINTESTINAL DISORDERS - Abdominal pain; Dry mouth; Dysphagia; Esophageal stenosis; Esophagitis; Gastritis; Gastroesophageal reflux disease; Oral pain

GENERAL DISORDERS AND ADMINISTRATION SITE CONDITIONS - Edema limbs; Malaise; Non-cardiac chest pain

IMMUNE SYSTEM DISORDERS - Allergic reaction

INVESTIGATIONS - Alkaline phosphatase increased; Blood bilirubin increased; CPK increased; GGT increased; INR increased; Lymphocyte count decreased; Neutrophil count decreased; Platelet count decreased; White blood cell decreased

METABOLISM AND NUTRITION DISORDERS - Acidosis; Hypoalbuminemia; Hypocalcemia; Hypomagnesemia; Hyponatremia

MUSCULOSKELETAL AND CONNECTIVE TISSUE DISORDERS - Back pain; Myalgia; Pain in extremity

NEOPLASMS BENIGN, MALIGNANT AND UNSPECIFIED (INCL CYSTS AND POLYPS) - Tumor hemorrhage

NERVOUS SYSTEM DISORDERS - Dizziness; Headache; Lethargy; Seizure

PSYCHIATRIC DISORDERS - Confusion; Insomnia

RENAL AND URINARY DISORDERS - Chronic kidney disease; Hematuria; Proteinuria

REPRODUCTIVE SYSTEM AND BREAST DISORDERS - Pelvic pain; Reproductive system and breast disorders - Other (female genital tract fistula)

RESPIRATORY, THORACIC AND MEDIASTINAL DISORDERS - Bronchopulmonary hemorrhage; Oropharyngeal pain; Pleural effusion; Productive cough; Respiratory failure; Respiratory, thoracic and mediastinal disorders - Other (nasal dryness); Respiratory, thoracic and mediastinal disorders - Other (nasal inflammation)

SKIN AND SUBCUTANEOUS TISSUE DISORDERS - Alopecia

VASCULAR DISORDERS - Hypotension; Vasculitis

NOTE: Afatinib in combination with other agents could cause an exacerbation of any adverse event currently known to be caused by the other agent, or the combination may result in events never previously associated with either agent.

Rev.2/16

